10.7 Appendix 7: Country-specific Requirements

10.7.1 China-specific Requirements

Section 8 Study Assessments and Procedures

The information in this appendix is added to the main protocol to describe the blood volume collection for participants in China.

Parameters Collected per Participant	Screening Period	Double-Blind Treatment Period	Post-Treatment Follow-up	Total Collections	mL per Collection	Total (mL)/ Test
		V5 to V15	V16			
FPG	1	7	-	8	2	16
Fasting FFA and P1NP	-	3	-	3	2.5	7.5
PT and INR	1	-	-	1	1.8	1.8
Hepatitis screen (HBsAg, anti-HCV, and HCV [RNA])	1	-	-	1	8.5	8.5
Hematology laboratory tests and when applicable A1C	1	6	-	7	2	14
Chemistry laboratory tests, fasting lipid profile ^a , and when applicable apoA1, apoB, and hCG	1	4	-	5	3.5	17.5
Chemistry laboratory tests	-	2	-	2	2.5	5
TSH, FT4, and when applicable FSH	1	5	-	6	2.5	15
Acetoacetic acid and beta-hydroxybutyrate	-	6	-	6	5	30
IGF-1	1	5	-	6	2.5	15
ACTH	-	8	-	8	2	16
CTX	-	3	-	3	2.5	7.5
Fasting insulin	-	3	-	3	2	6
Adiponectin	-	3	-	3	2.5	7.5
Blood for serum MK-3655 PK assay (for PK only timepoint)	-	1	-	1	2	2
Blood for serum MK-3655 PK assay and immunogenicity assay (ADA)	-	5	1	6	4	24
Total Blood Volume per Participant ^b						193.3 mL
A1C=glycated hemoglobin; ACTH=adrenocorticotrophic hormone; ADA=anti-drug antibodies; apoA1=apolipoprotein A1; apoB=apolipoprotein B; CTX=collagen type 1 cross-linked telopeptide; EOT=end of treatment; FFA=free fatty acid; FPG=fasting plasma glucose; FT4=free thyroxine; FSH=follicle stimulating hormone; HBsAg=Hepatitis B surface antigen; hCG=human chorionic gonadotropin; HCV=Hepatitis C virus; HDL-C=high density lipoprotein-cholesterol; IGF-1=insulin-like growth factor-1; INR=international normalized ratio; LDL-C=low density lipoprotein-cholesterol; P1NP=procollagen type 1 N-terminal propeptide; PK=pharmacokinetic; PT=prothrombin time; RNA=ribonucleic acid; TG=triglycerides; TSH=thyroid-stimulating hormone; V=visit.						
^a Includes total cholesterol, non-HDL-C, HDL-C, LDL-C, and TG.						
^b If additional pharmacokinetic/pharmacodynamic and/or safety analyses are necessary, additional blood (up to 50 mL) may be obtained.						

10.7.2 Argentina-specific Requirements

Section 1.3 Schedule of Activities (SoA), Section 8.11.3.1 Visit 1/Screening and Section 10.2 Appendix 2: Clinical Laboratory Tests

All participants at study sites in Argentina must be tested for Hepatitis B, Hepatitis C, and HIV at Visit 1/Screening before randomization.

10.7.3 Taiwan-specific Requirements

Section 1.1 Synopsis, Section 1.2 Schema, Section 3 Hypotheses, Objectives, and Endpoints, Section 4.1 Overall Design, Section 5 Study Population and Section 5.1 Inclusion Criteria

All participants at study sites in Taiwan must be a male or female aged 20 years to 80 years with capacity of will, at the time of signing the ICF.

10.7.4 Japan-specific Requirements

Section 1.1 Synopsis, Section 1.2 Schema, Section 3 Hypotheses, Objectives, and Endpoints, Section 4.1 Overall Design, Section 5 Study Population, and Section 5.1 Inclusion Criteria

All participants at study sites in Japan must be a male or female aged 20 years to 80 years, at the time of signing the ICF.

Section 1.3 Schedule of Activities (SoA), Section 6.1 Study Intervention(s) Administered, Section 6.4 Study Intervention Compliance, Section 8.1.8.3 Self-injection Training (Participant and/or Caregiver), Section 8.1.8.4 Witnessed Dosing, Section 8.1.9 Study Intervention Administration, Section 8.1.9.1 Timing of Dose Administration, and Section 8.6.1 Blood Collection for Serum MK-3655

In Japan, administration of study intervention can only be performed by a medically qualified person (eg, physician, supporting nurse); self-administration by the participant him/herself is the only exception. Therefore, administration of study intervention by a caregiver will not be allowed in Japan.

Section 4.1 Overall Design and 6.3.2 Stratification

If either proportion of participants, those with T2DM or those without T2DM, exceeds approximately 60% of the total targeted sample size, the remaining participants enrolled will be restricted to the other stratum within this stratification factor. In Japan, enrollment will not be restricted by this cap, and sites will be able to continue to enroll participants with or without T2DM.

Section 5.2 Exclusion Criteria, Section 7.1 Discontinuation of Study Intervention, Section 10.2 Appendix 2: Clinical Laboratory Tests, and Section 10.13 Appendix 13: eGFR Equations

For the calculation of eGFR for participants in Japan, the Japanese 3-variable Equation 4 will be used (see Appendix 13) [Matsuo, S., et al 2009].

10.7.5 Korea-specific Requirements

Section 5.2 Exclusion Criteria

Prior/Concurrent Clinical Study Experience

23. Is currently participating in or has participated in an interventional clinical study with an investigational compound or device ≤ 3 months **or** ≤ 5 half-lives (**whichever is longer**) before participating in this current study. Participants enrolled in observational studies may be included and will be reviewed on a case-by-case basis for approval by the Sponsor.

10.8 Appendix 8: Other Medical Device: Complaints Including Product Quality Complaint, Malfunction, Serious Injury, Death, Fetal Distress/Fetal Death and Congenital Anomaly: Definitions and Reporting

Not applicable.

10.9 Appendix 9: Approximate Blood Volume Table

Parameters Collected per Participant	Screening Period	Double-Blind Treatment Period	Post-Treatment Follow-up	Total Collections	mL per Collection	Total (mL)/Test
		V5 to V15	V16			
FPG	1	7	-	8	2	16
Fasting FFA and P1NP	-	3	-	3	2.5	7.5
PT and INR	1	-	-	1	1.8	1.8
Hepatitis screen (HBsAg, anti-HCV, and HCV [RNA])	1	-	-	1	8.5	8.5
Hematology laboratory tests and when applicable A1C	1	6	-	7	2	14
Chemistry laboratory tests, fasting lipid profile ^a , and when applicable apoA1, apoB, and hCG	1	4	-	5	3.5	17.5
Chemistry laboratory tests	-	2	-	2	2.5	5
TSH, FT4, and when applicable FSH	1	5	-	6	2.5	15
Acetoacetic Acid	-	6	-	6	6	36
Beta-hydroxybutyrate	-	1	-	1	2.5	2.5
Beta-hydroxybutyrate and IGF-1	-	5	-	5	2.5	12.5
IGF-1	1	-	-	1	2.5	2.5
ACTH	-	8	-	8	2	16
CTX	-	3	-	3	2.5	7.5
Adiponectin	-	3	-	3	2.5	7.5
Fasting insulin	-	3	-	3	2	6
Pro-C3	-	3	-	3	2.5	7.5
Blood for serum biomarkers	1	5	-	6	4	24
Blood for plasma biomarkers	1	5	-	6	6	36
Blood for serum MK-3655 PK assay (for PK only timepoint)	-	1	-	1	2	2
Blood for serum MK-3655 PK assay and immunogenicity assay (ADA)	-	5	1	6	4	24
Blood for planned genetic analysis	-	1	-	1	8.5	8.5
Total Blood Volume per Participant ^b						277.8 mL

A1C=glycated hemoglobin; ACTH=adrenocorticotropic hormone; ADA=anti-drug antibodies; apoA1=apolipoprotein A1; apoB=apolipoprotein B; CTX=collagen type 1 cross-linked telopeptide; EOT=end of treatment; FFA=free fatty acid; FPG=fasting plasma glucose; FT4=free thyroxine; FSH=follicle stimulating hormone; HBsAg=Hepatitis B surface antigen; hCG=human chorionic gonadotropin; HCV=Hepatitis C virus; HDL-C=high density lipoprotein-cholesterol; IGF-1=insulin-like growth factor-1; INR=international normalized ratio; LDL-C=low density lipoprotein-cholesterol; P1NP=procollagen type 1 N-terminal propeptide; PK=pharmacokinetic; Pro-C3=propeptide of type III collagen; PT=prothrombin time; RNA=ribonucleic acid; TG=triglycerides; TSH=thyroid-stimulating hormone; V=visit.

^a Includes total cholesterol, non-HDL-C, HDL-C, LDL-C, and TG.

^b If additional pharmacokinetic/pharmacodynamic and/or safety analyses are necessary, additional blood (up to 50 mL) may be obtained.

10.10 Appendix 10: Management of Participants With Elevated Liver Enzymes

Although participants enrolled in this study will have baseline liver disease, their hepatic function should not be significantly impaired. However, at baseline, some may have liver biochemistry levels above the ULN.

The central laboratory report will alert the investigator if a participant meets the thresholds outlined in Section 8.4.7. The investigator should initiate close observation and discontinue the participant from blinded study intervention if a prespecified criterion for discontinuation is met.

Close Observation for DILI Guidelines:

- Repeating liver biochemistries (ALT, AST, ALP, total bilirubin, INR) within 48 hours
- Obtaining a more detailed history of symptoms and prior or concurrent disease
- Obtaining a history of concomitant drug use (including nonprescription medications and herbal and dietary supplement preparations), alcohol use, recreational drug use, and special diets
- Obtaining a history of exposure to environmental chemical agents
- Ruling out other causes of liver disease as needed (obtain viral hepatitis panel, imaging for evaluation of biliary tract disease, etc. if required in the opinion of the primary investigator)
- Continuing to monitor liver biochemistries twice weekly. Frequency can decrease to once a week or less if abnormalities stabilize or study intervention has been discontinued and participant is asymptomatic
- Reviewing *Discontinuation of Study Intervention for Elevated Liver Enzymes* (see below) to see if a participant meets a given criterion
- Considering a gastroenterology or hepatology consultation
- Considering a liver biopsy

Discontinuation of Study Intervention for Elevated Liver Enzymes

However, for all participants, study intervention should be discontinued if any of the specified criteria below are met and no other cause for the combination of laboratory abnormalities is immediately apparent:

For participants with ALT and AST \leq ULN at baseline who meet ANY of the following criteria:

- ALT or AST $>3 \times$ ULN **AND** either total bilirubin $>2 \times$ ULN or INR $>1.5^*$
- ALT or AST $>3 \times$ ULN **AND** the appearance of fatigue, nausea, vomiting, right upper quadrant pain or tenderness, fever, rash, and/or eosinophilia ($>5\%$)

- ALT or AST $>5 \times$ ULN for more than 2 weeks
- ALT or AST $>3 \times$ ULN **AND** participant is unwilling or unable to undergo repeat ALT and AST testing at the frequency defined above in the *Close Observation for DILI Guidelines*
- ALT or AST $>8 \times$ ULN (confirmed by repeat testing)

For participants with ALT and/or AST $>ULN$ at baseline** who meet ANY of the following criteria:

- ALT and/or AST $>2 \times$ baseline **AND** total bilirubin $>2 \times$ ULN or INR $>1.5^*$ (confirmed by repeat testing)
- ALT and/or AST $>2 \times$ baseline **AND** the appearance of fatigue, nausea, vomiting, right upper quadrant pain or tenderness, fever, rash, and/or eosinophilia ($>5\%$) (confirmed by repeat testing)
- ALT and/or AST $>5 \times$ baseline for more than 2 weeks
- ALT and/or AST $>3 \times$ baseline **AND** participant is unwilling or unable to undergo repeat ALT and AST testing at the frequency defined above in the *Close Observation for DILI Guidelines*
- ALT and/or AST ≥ 500 U/L (confirmed by repeat testing)

***Note:** For participants who initiate anticoagulant therapy after study initiation, the INR threshold does not apply.

****Note:** If only one of the analytes (ie, ALT or AST) was $>ULN$ at baseline, each criterion below would only apply to the analyte that was $>ULN$ at baseline.

10.11 Appendix 11: Patient Health Questionnaire - 9

PATIENT HEALTH QUESTIONNAIRE-9 (PHQ-9)				
Over the last 2 weeks , how often have you been bothered by any of the following problems? (Use "✓" to indicate your answer)	Not at all	Several days	More than half the days	Nearly every day
1. Little interest or pleasure in doing things	0	1	2	3
2. Feeling down, depressed, or hopeless	0	1	2	3
3. Trouble falling or staying asleep, or sleeping too much	0	1	2	3
4. Feeling tired or having little energy	0	1	2	3
5. Poor appetite or overeating	0	1	2	3
6. Feeling bad about yourself — or that you are a failure or have let yourself or your family down	0	1	2	3
7. Trouble concentrating on things, such as reading the newspaper or watching television	0	1	2	3
8. Moving or speaking so slowly that other people could have noticed? Or the opposite — being so fidgety or restless that you have been moving around a lot more than usual	0	1	2	3
9. Thoughts that you would be better off dead or of hurting yourself in some way	0	1	2	3
FOR OFFICE CODING  0  +   +   +   =Total Score:  				
If you checked off any problems, how difficult have these problems made it for you to do your work, take care of things at home, or get along with other people?				
Not difficult at all 	Somewhat difficult 	Very difficult 	Extremely difficult 	

Developed by Drs. Robert L. Spitzer, Janet B.W. Williams, Kurt Kroenke and colleagues, with an educational grant from Pfizer Inc. No permission required to reproduce, translate, display or distribute.

10.12 Appendix 12: NASH Clinical Research Network (CRN) Scoring System for Determining Eligibility and Assessing Secondary Histological Endpoints

NAFLD Activity Score (NAS)		Fibrosis Staging	
Parameter	Scoring Criteria	Parameter	Staging Criteria
Steatosis	0 = <5% 1 = 5% to 33% 2 = >33% to 66% 3 = >66%	Stage 0	No Fibrosis
Lobular Inflammation	0 = No Foci 1 = <2 Foci per 200 × field 2 = 2 to 4 Foci per 200 × field 3 = >4 Foci per 200 × field	Stage 1 Stage 1a Stage 1b Stage 1c	Perisinusoidal or Periportal Mild, Zone 3, Perisinusoidal Moderate, Zone 3, Perisinusoidal Portal / Periportal
Ballooning	0 = None 1 = Few Balloon Cells 2 = Many Cells / Prominent Ballooning	Stage 2	Perisinusoidal and Portal / Periportal
		Stage 3	Bridging Fibrosis
		Stage 4	Cirrhosis

Source ID: [Kleiner, D. E., et al 2005]

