The following laboratory abnormalities are exceptions to #6 and #7. For these events, CTCAE severity grading will not be used as a basis for a participant to be discontinued from study intervention. The requirements for a participant to be discontinued from study intervention are listed for each laboratory abnormality.

- **Abnormalities of ALT and/or AST:** If the participant has abnormal ALT and/or AST meeting criteria specified in Appendix 10 and no other cause for the combination of laboratory abnormalities is immediately apparent (eg, prolonged INR with warfarin use), study intervention will be discontinued.

Note: See Appendix 10 for additional details on management of blinded study intervention for participants with elevated liver enzymes.

- **Reduction of renal function:** If the participant has an eGFR that is persistently $<30 \text{ mL/min/1.73 m}^2$ as calculated by the MDRD formula, study intervention will be discontinued. For participants in Japan, eGFR will be calculated with the Japanese 3-variable Equation 4 (Appendix 7) [Matsuo, S., et al 2009]. See Appendix 13 for the eGFR equations.

Note: A persistent eGFR value is defined as a repeat measurement, performed within 2 weeks after notification from the central laboratory, that remains $<30 \text{ mL/min/1.73 m}^2$, despite correction of potential causative factors (eg, correction of volume depletion, discontinuation of NSAIDs). If the eGFR value continues to meet the discontinuation criterion but demonstrates stability or improvement relative to the prior result, an additional repeat measurement may be performed within 7 days.

- **Salivary cortisol:** If the participant has a bedtime salivary cortisol test value $>1.5 \times \text{ULN}$ **AND** $>50\%$ above baseline during the study, a repeat bedtime salivary cortisol will be obtained. If the second test value is also $>1.5 \times \text{ULN}$ **AND** $>50\%$ above baseline, a 24-hour urinary cortisol test will be performed. If the 24-hour urinary cortisol value is elevated $>1 \times \text{ULN}$, study intervention will be discontinued (see Section 8.3.9.1).

Note: The baseline assessment for the salivary cortisol test value is considered the one closest to but before dosing (Visit 5/Randomization [Day 1]). However, if no sample is collected before the Visit 5/Randomization, the Visit 1/Screening test value should be used for the baseline assessment.

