8.4.7 Events of Clinical Interest (ECIs)

Selected nonserious and SAEs are also known as ECIs and must be reported to the Sponsor.

Events of clinical interest for this study include:

1. For participants with ALT and AST \leq ULN at baseline who meet ANY of the following criteria*:
 - ALT or AST $>3 \times$ ULN
 - Total bilirubin $>2 \times$ ULN (if direct bilirubin is elevated)
 - Alkaline phosphatase $>3 \times$ ULN
 - INR $>1.5 \times$ ULN**
 - Clinical signs or symptoms that are, in the opinion of the investigator, consistent with hepatitis (such as right upper quadrant discomfort, fever, nausea, vomiting, jaundice, rash, or eosinophilia $>5\%$)
2. For participants with ALT and/or AST $>$ ULN at baseline who meet ANY of the following criteria*:
 - ALT and/or AST $>2 \times$ baseline***
 - Total bilirubin $>1.5 \times$ baseline AND $>$ ULN (if direct bilirubin is elevated)
 - Alkaline phosphatase $>3 \times$ ULN
 - INR $>1.5 \times$ ULN**

- Clinical signs or symptoms that are, in the opinion of the investigator, consistent with hepatitis (such as right upper quadrant discomfort, fever, nausea, vomiting, jaundice, rash, or eosinophilia >5%).

*Note: The purpose of the criteria is to specify a threshold of abnormal hepatic tests that may require an additional evaluation for an underlying etiology. The study site guidance for assessment and follow-up of these criteria can be found in the Investigator Study File Binder (or equivalent). During a period of close observation for DILI, study intervention can be continued, if desired, at the discretion of investigator in consultation with the Sponsor Clinical Director.

**Note: For participants who initiate anticoagulant therapy after study initiation, the INR threshold does not apply.

***Note: If only one of the analytes (ie, ALT or AST) was >ULN at baseline, this criterion (ie, >2 × baseline) would only apply to the analyte that is >ULN at baseline while the criterion noted under #1 above (ie, >3 × ULN) would apply to the analyte that was ≤ULN at baseline.

3. Suicidal ideation, suicidal behaviors

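### Appendix 10 sets no ALT/AST stopping threshold for the enzyme that was normal at baseline when only the other one was raised

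*Combined protocol and SAP*

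**What the plan says.** Section 7.1 makes Appendix 10 (Section 10.10) the stopping rule for abnormal ALT or AST. It lists these abnormalities as exceptions to the general laboratory rules #6 and #7, for which "CTCAE severity grading will not be used as a basis for a participant to be discontinued from study intervention".

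Appendix 10 states that "for all participants, study intervention should be discontinued if any of the specified criteria below are met", provided no other cause is immediately apparent. Two lists of five criteria follow.

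- **List 1** is for participants with ALT and AST both at or below ULN at baseline. Its thresholds are multiples of ULN.
- **List 2** is for participants with ALT and/or AST above ULN at baseline. Its thresholds are multiples of baseline, plus an absolute limit of 500 U/L.

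The ** note attached to list 2 deals with the mixed case of exactly one raised enzyme: "each criterion below would only apply to the analyte that was" above ULN at baseline. It says nothing about the other enzyme.

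Section 8.4.7 (Events of Clinical Interest) uses the same two groups. Its *** note also restricts the multiple-of-baseline criterion to the raised enzyme, but then continues: "while the criterion noted under #1 above" (more than 3 × ULN) applies to the enzyme that was normal. Meeting an 8.4.7 threshold leads to reporting and close observation. During close observation, "study intervention can be continued, if desired, at the discretion of investigator in consultation with the Sponsor Clinical Director".

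**The concern.** A participant with one raised and one normal enzyme is outside list 1 by its heading and inside list 2. The ** note then confines every list 2 criterion, including the 500 U/L limit, to the enzyme that was raised. Nothing in Appendix 10 sends the normal enzyme back to list 1. Read literally, that enzyme has no prespecified threshold at which drug must stop.

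The mixed state is eligible: Table 2 in Section 5.2 excludes only ALT or AST above 5 × ULN, and both notes anticipate it. What is at stake is participant safety under a rule meant to be objective. A large rise in the normal enzyme together with raised bilirubin could leave an investigator who works through the list with the answer that no criterion is met.

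**Working it through.** The plan states no figure on this point, so there is none to reproduce. The check applies both lists, as written, to one laboratory picture.

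**Inputs.** The criteria come from Appendix 10. The enzyme course is illustrative. ULN in U/L is not given, so 30, 40 and 50 are assumed where the 500 U/L limit needs a value. Baseline: ALT 0.9, AST 1.2 × ULN. Later: ALT 10, AST 2.4, bilirubin 3 × ULN, confirmed on repeat; INR not raised, no symptoms, repeat testing accepted, duration not over 2 weeks.

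**Step 1: the two lists side by side.** List 1 is shown as it would apply had both enzymes been normal at baseline. List 2 is shown as limited by the ** note, so only AST counts: 2.4 / 1.2 = 2.0 × baseline.

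| Criterion | List 1 | List 2, AST only |
|---|---|---|
| Enzyme with bilirubin or INR | ALT 10 > 3 and bilirubin 3 > 2: met | 2.0 is not > 2: not met |
| Enzyme with symptoms | no symptoms: not met | 2.0 is not > 2: not met |
| Sustained over 2 weeks | not sustained: not met | 2.0 is not > 5: not met |
| Repeat testing refused | accepted: not met | 2.0 is not > 3: not met |
| High value, confirmed | ALT 10 > 8: met | AST 72, 96 or 120 U/L, below 500: not met |
| **Total** | **2 of 5** | **0 of 5** |

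**Step 2: when the gap opens.** If the raised enzyme is at or below 2 × its baseline and below 500 U/L, with INR not raised, no list 2 criterion can be met, however high the other enzyme or bilirubin. For baseline AST of 1.2, 2.0 or 3.0 × ULN, that ceiling is 2.4, 4.0 or 6.0 × ULN, or 72 to 300 U/L over the assumed ULNs (2.4 × 30 to 6.0 × 50). This condition is sufficient, not necessary. With AST from 1.5 to 3.1 × ULN (2.07 × baseline), ALT 9 × ULN and neither raised bilirubin nor symptoms, list 2 is still not met, while ALT above 8 × ULN, if confirmed, is a list 1 criterion.

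**Step 3: when it closes.** In the Step 1 example with AST at 2.41 × ULN, 2.41 / 1.2 = 2.008 > 2. With bilirubin 3 × ULN, confirmed, list 2 is met and drug stops.

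**Step 4: comparison with both raised.** Had both started at 1.2 × ULN, ALT would be 10 / 1.2 = 8.3 × baseline with bilirubin above 2 × ULN, and list 2 would be met. This does not hold at every raised baseline. ALT from 5 to 10 × ULN is exactly 2.0 × baseline and, at a ULN of 40, 10 × 40 = 400 U/L. With AST also at or below 2 × baseline and below 500 U/L, list 2 gives 0 of 5.

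**Step 5: with the missing clause added.** Sending ALT to list 1 gives the two criteria met in Step 1 (above 3 × ULN with bilirubin; above 8 × ULN confirmed): 2 instead of 0.

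**The case against.** The strongest reply is that the participant is not unprotected, and this stands. "The central laboratory report will alert the investigator if a participant meets the thresholds outlined in Section 8.4.7", and those thresholds do cover the normal enzyme at more than 3 × ULN. Repeat tests within 48 hours and twice-weekly monitoring follow (Appendix 10), and potential drug-induced liver injury is reported within 24 hours (Table 4). Section 7.1 #2 requires discontinuation once the investigator and/or Sponsor judges the risk unnecessary. Rules #4 and #5 still cover clinical adverse events. Rules #6 and #7 still cover bilirubin and INR, which are not among the exceptions, although they depend on medical intervention or hospitalization. The eDMC reviews safety (Section 9.7), and four-weekly dosing leaves time before the next injection. A reader might infer that nothing could stop drug in such a participant; the documents do not support that. But none of these is an ALT/AST threshold stop.

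Judgement also enters both lists, since a criterion counts only if no other cause is immediately apparent. That softens the contrast with discretion but does not supply the missing threshold.

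The example needs ALT to rise about 11-fold (10 / 0.9) while AST no more than doubles, and nothing shows how often that happens. This is fair: the calculation shows what the rule does, not how often it matters.

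Section 8.4.7 adds that "The study site guidance for assessment and follow-up of these criteria can be found in the Investigator Study File Binder". That guidance is not in the documents and may deal with mixed baselines. It would still be better for Appendix 10, which Section 7.1 makes the rule, to say so itself.

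It might be said that investigators would apply list 1 to the normal enzyme anyway. The list 1 heading does not allow it.

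**Conclusion.** The point holds in limited form. With exactly one of ALT and AST above ULN at baseline, the enzyme that was normal has no prespecified ALT/AST stopping threshold, and this matters only when the raised enzyme itself meets no list 2 criterion. In the worked example the count is 0 of 5, against 2 of 5 had both been normal.

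Assumptions: an illustrative enzyme course; ULN of 30 to 50 U/L; and INR not raised. The last matters because the first list 2 criterion lacks the word that in list 1 ties INR to the enzyme rise, so raised INR alone could be read as a trigger.

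Three stronger readings are not supported. First, Appendix 10 and Section 8.4.7 do not contradict each other: one governs stopping and the other reporting, and the 8.4.7 note suggests that Appendix 10 simply omits its second half. Second, a mixed-baseline participant is not always less protected than one with both enzymes raised (Step 4). Third, no effect on any endpoint follows. The position of the ** note relative to its list is not counted as an error.

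Confidence is high on the wording and lower on practice, because frequency cannot be estimated and the site guidance is unseen. It is a drafting omission in a liver-safety rule and should be corrected.

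**What to change.** Reword the ** note along these lines: *Where exactly one of ALT and AST exceeded ULN at baseline, the criteria in this list apply to that analyte only. The other analyte is judged by the criteria for participants whose ALT and AST were both at or below ULN at baseline, including the \* note on INR.*

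This follows the logic of the *** note in Section 8.4.7. It also keeps the existing exemption: "For participants who initiate anticoagulant therapy after study initiation, the INR threshold does not apply".

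The cost is a one-note protocol clarification, a matching check of the site liver-monitoring guidance, and possibly a few more study-drug discontinuations.
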